Obese patients represent an evident challenge in anesthetic management due to their higher risks of difficult intubation and ventilation, impaired pulmonary functions, difficult vascular access, and delayed recovery from anesthesia.¹⁰ (Figure 1) Study has showed the risk of difficult tracheal intubation is higher in obese patients with a three times higher risk compared to the nonobese.¹¹ Besides, obese patients have multiple respiratory abnormalities, including reduced vital capacity, inspiratory capacity, expiratory reserve volume, functional residual capacity, and lower lung compliance.¹² Obesity is also the greatest risk factor for obstructive sleep apnea (OSA)¹³, which predisposes obese patients to higher risks of difficult ventilation and rapid oxygen desaturation during induction of general anesthesia.¹⁴ Study has showed the nonhypoxic apnea time of peripheral oxygen saturation (SpO₂) decreasing to 90% after facemask preoxygenation is less than 3 minutes in obese patients compared to 6 minutes in patients having a normal BMI.¹⁵ In addition to respiratory complications in anesthesia, morbidly obese patients are prone to have a difficult arterial puncture because of their excessive subcutaneous tissue and higher risk of vascular complication after arterial puncture.¹⁶

Morbidly obese patients are susceptible to low emergence from anesthesia due to delayed release of volatile agent from excessive adipose tissue.¹⁷ They have an increased risk of lingering respiratory depression effects of anesthetic drugs. However, the current Enhanced Recovery After Surgery (ERAS) protocol does not recommend specific anesthetic agents for bariatric surgery due to mixed results of available studies.¹⁸ Some studies showed desflurane has

consistent and rapid recovery profile compared to sevoflurane and propofol.¹⁹⁻²¹ Conversely, other studies reported that the difference in immediate recovery between desflurane and sevoflurane is clinically non-significant.²² Moreover, although electroencephalography (EEG)-based monitoring of anesthesia depth is widely used and effective in maintaining the optimal range of anesthesia depth in total intravenous anesthesia, there is sparse evidence regarding the role of EEG-based monitoring in volatile general anesthesia for obese patients.²³

Difficult Laryngoscopy Intubation

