Recovery from anesthesia might be compromised in obese patients due to delayed release of volatile anesthetics from excessive fat tissue.¹⁷ However, evidence regarding optimal anesthesia strategy to enhance obese patients' recovery is still insufficient and conflicting.¹⁸ Randomized trial has showed that anesthetic maintenance using desflurane achieves more rapid postoperative immediate and intermediate recoveries than propofol or isoflurane anesthesia.¹⁹ Similarly, another study reported obese patients receiving bispectral index(BIS)-guided desflurane anesthesia had faster immediate recovery, eye opening, extubation, airway maintenance, and orientation compared to sevoflurane anesthesia.²⁰ However, other investigators claimed that the differences in immediate recovery between desflurane and sevoflurane are not clinically significant.^{22,46}

Meta-analysis has showed that BIS-guided anesthesia may enhance early recovery times in patients undergoing surgery under general anesthesia compared to clinical signs.⁴⁷ However, few studies have investigated whether anesthesia with EEG-based monitoring of anesthesia depth improves the postoperative recovery in obese patients. Ibraheim and colleagues reported that patients receiving BIS-guided sevoflurane anesthesia had significantly faster awakening and shorter extubation time, and lower sevoflurane consumption and cost compared to the control group.⁴⁸ However, this study had a small patient sample and did not evaluate other volatile anesthetics, such as desflurane anesthesia.⁴⁸

Eligible Criteria

Adult obese patients (BMI \geq 30 kg/m²) undergoing LSG at Shuang Ho Hospital, Taipei Medical University will be included. Exclusion criteria will be severe cardiopulmonary disease, psychiatric disorder, history of head and neck surgery or radiation therapy, cervical spine injury,

renal insufficiency (estimated creatinine clearance < 60 ml/min), $\text{SpO}_2 < 90\%$ in room air, hemodynamic instability, preexisting arterial catheterization during the same visit within 7 days, and patient refusal.

Objectives of Study

The main objective of this study is to investigate the optimal anesthesia strategy in the airway evaluation, preoxygenation, arterial cannulation, and choice of volatile anesthetics in obese patients undergoing bariatric surgery, as the followed:

1. To explore potential predictors for difficult intubation using ultrasound evaluation of upper airway anatomy and tongue base

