Patients will be randomized by a computer-generated list into one of the four groups, desflurane with usual care (N=20), desflurane with M-Entropy guidance (N=20), sevoflurane with usual care (N=20), and sevoflurane with M-Entropy guidance (N=20). At the operating room, a M-Entropy™ sensor and S/5™ module (GE Healthcare, Helsinki, Finland) will be applied to all patients' forehead before induction of anesthesia according to the manufacturer's recommendations. This will be connected to a M-Entropy Monitor that will be concealed from the patients and operators.

In the M-Entropy group, dosage of volatile anesthetics will be adjusted to achieve the Response and State Entropy value between 40 and 60 from the start of anesthesia to the end of surgery. In the usual care group, dosage of volatile anesthetics will be titrated according to clinical judgment. This will be to maintain arterial pressure within 20% range of the baseline and the heart rate within the range 50 to 100 beats/min. In case of signs of inadequate anesthesia (e.g. movement, cough and swallowing), anesthetic dose will be increased. M-Entropy monitoring will be continued in the usual care group, but the Entropy number and EEG waveform will be concealed from the anesthetist in charge. Entropy values, hemodynamic, and expiratory gas data will be recorded in 5-min intervals. In all patients, cessation of general anesthesia will be timed to facilitate early awakening after wound closure. All patients will be decurarized from rocuronium-induced neuromuscular blockade with sugammadex dosed at 2 mg/kg ideal body weight + 40%.⁶³ Primary outcome is time to spontaneous eye opening. Secondary outcomes include time to tracheal extubation, time to orientation in time and place, and time to leave operating room, event of emergence agitation. The Richmond Agitation-Sedation Scale (RASS) will be used to evaluate the level of agitation and sedation promptly after extubation.⁶⁴ For patients who are transferred to the intensive care unit for postoperative mechanical ventilation, the investigators will record the time to extubation.

Statistical Analysis Plan

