The distributions of baseline patient characteristics and outcome variables will be compared between two groups using chi-square tests or Fisher's exact test for categorical variables and either t tests or Wilcoxon rank sum tests for continuous variables, as appropriate. For four-group comparisons, either ANOVA tests or Kruskal-Wallis tests will be used for continuous variables, as appropriate. A Bonferroni correction to the significance criterion for multiple comparisons is applied where appropriate. For time to event data, Kaplan-Meier method and log-rank test will be applied for group comparisons. Multivariable logistic regression, simple linear regression, or Cox proportional hazards regression analyses will be used to identify potential influential factors of outcomes of interest. A two-sided significance level of 0.05 was used to define statistically significant difference. All the statistical analyses will be conducted using Statistics Analysis System (SAS), Version 9.4 (SAS Institute Inc., Cary, NC, USA).

According to prior study³⁷, at least 37 patients in each group of HFNC or facemask preoxygenation are needed to detect a difference of 30 seconds of nonhypoxic apnea time between the HFNC and facemask group, accepting a type I error of 5% and type II error of 20% with anticipated nonhypoxic apnea time of mean $188 \pm SD 46$ seconds in the facemask group.⁶⁵ Nevertheless, in order to allocate 20 patients into each group of volatile anesthesia with desflurane or sevoflurane with or without M-Entropy guidance, a total of 80 patients will be enrolled in this study.

TMU-JIRB Form059/20180201
Protocol Number: N202002076
Version : 4
Date : 2020.04.08

There are about 120 patients undergoing LSG at our hospital per year. Considering the patient selection criteria and possible patient refusal, a total of 50 patients per year will be enrolled in this study. Therefore, it will take about 2 years for patient recruitment. Besides, the investigators will select all randomized subjects for analysis.

Reference

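### Substudy 4 compares recovery times without adjusting for BMI, which is known for every patient and which the protocol itself links to slow emergence, so precision may be lost in the trial's smallest groups (20 per cell)

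*Combined protocol and SAP*

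**What the plan says.** Study Protocol, Substudy 4, randomises 80 patients to four cells of 20 (desflurane or sevoflurane, each with usual care or M-Entropy guidance). It states: "Primary outcome is time to spontaneous eye opening".

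The Statistical Analysis Plan section says "For time to event data, Kaplan-Meier method and log-rank test will be applied for group comparisons". For continuous outcomes it names t or Wilcoxon tests for two groups and ANOVA or Kruskal-Wallis for four. None of these carries a covariate or a stratum. The next sentence plans logistic, linear and Cox regression, but to identify factors that influence outcomes. It does not present them as the treatment comparison and does not name BMI.

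On body fat, the Background section on obesity as an anesthetic challenge says that morbidly obese patients tend to emerge slowly "due to delayed release of volatile agent from excessive adipose tissue". The section on delayed recovery is more cautious: "Recovery from anesthesia might be compromised in obese patients due to delayed release of volatile anesthetics from excessive fat tissue".

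Eligible Criteria require a BMI of at least 30 kg/m² and state no upper limit. The randomisation is described as computer-generated and in permuted blocks, with no mention of stratification by BMI.

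**The concern.** The protocol gives a biological reason why fatter patients may wake later, and BMI is available before randomisation for everyone enrolled. If BMI does predict eye-opening time within this population, an unadjusted comparison leaves that variation in the error term.

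Substudy 4 is where this would matter most. Its cells hold 20 patients, against arms of 40 in Substudies 2 and 3, and its size is not backed by any stated effect, SD or power. At stake is some power for the primary comparison. There is also a pre-specification point: if BMI turns out to differ between cells, a decision to adjust that is taken after seeing the difference would be data-driven.

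**Working it through.** **The plan's own figure.** The only calculated sample size is for Substudy 3, "to detect a difference of 30 seconds of nonhypoxic apnea time between the HFNC and facemask group", with SD 46 s, two-sided 5% and 80% power:

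n = 2 × 46² × (1.960 + 0.842)² / 30² = 36.9, rounded up to 37 per group.

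This matches the stated 37. It does not bear on Substudy 4, where 20 per cell is an allocation target only.

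**Inputs for Substudy 4.** From the documents: cells of 20, and "A two-sided significance level of 0.05 was used to define statistically significant difference". Assumed, because the documents give neither: an effect of 0.6 SD on log time, and a correlation r between BMI and log eye-opening time of 0 to 0.5 within BMI of 30 or more.

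**Formula.** In a linear model, adjustment multiplies the residual variance by 1 − r², so the standardised effect becomes 0.6/√(1 − r²). Power comes from the noncentral t distribution with noncentrality [0.6/√(1 − r²)] × √(n/2), where n is the number per group. For example, at r = 0.3 and n = 20 the effect is 0.6/√0.91 = 0.629 and the noncentrality is 0.629 × √10 = 1.99, giving 49% power.

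| r | 1 − r² | Equivalent cell size, 20/(1 − r²) | Power, 20 vs 20 | Power, 40 vs 40 |
|---|---|---|---|---|
| unadjusted | 1 | 20.0 | 46% | 76% |
| 0.1 | 0.99 | 20.2 | 46% | 76% |
| 0.2 | 0.96 | 20.8 | 47% | 77% |
| 0.3 | 0.91 | 22.0 | 49% | 79% |
| 0.4 | 0.84 | 23.8 | 52% | 82% |
| 0.5 | 0.75 | 26.7 | 57% | 86% |

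The 40 vs 40 column is each randomised factor averaged over the other, an analysis the plan does not name.

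**Cost.** One degree of freedom. Estimating the BMI slope with 80 patients in four cells inflates the variance by about 1/74, or 1.4%. The net variance ratio is 0.99 × 1.014 ≈ 1.00 at r = 0.1 and 0.91 × 1.014 ≈ 0.92 at r = 0.3. The gain therefore disappears at r of about 0.1 or less.

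**Log-rank and Cox.** The 1 − r² factor does not carry over to these. A simulation (3,000 uncensored log-normal trials per setting, 20 vs 20, effect 0.886 SD, which is the unadjusted detectable difference at 80% power by the normal approximation) gave:

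| r | Unadjusted Cox (close to log-rank) | BMI-adjusted Cox | Linear model on log time with BMI |
|---|---|---|---|
| 0 | 72% | 72% | 78% |
| 0.3 | 71% | 76% | 82% |
| 0.5 | 71% | 83% | 87% |

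The row at r = 0 shows that part of the linear model's advantage comes from the assumed log-normal times and not from BMI. With no treatment effect and r = 0.3, rejection rates were 5.2%, 6.2% and 4.6% in the same order.

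**Chance imbalance.** Between two cells of 20, the difference in mean BMI has an SD of √(2/20) = 0.32 BMI SDs. The chance that it exceeds 0.5 SD is 11% for a given pair of cells and about 39% for at least one of the six pairs. For 40 vs 40 it is 2.5%.

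**The case against.** The strongest reply is that no loss has been demonstrated. Both Background passages describe obese patients as a group, one of them only as a possibility, and neither gives a gradient of recovery time with BMI above 30. The BMI spread is not given either. Substudy 4 also offers reasons for a weak gradient: the agent is titrated to Entropy or to hemodynamics, and its cessation is timed to facilitate early awakening. This stands. The documents do not support saying that precision is lost, only that it may be.

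A reader might also infer that BMI imbalance in small cells biases the comparison. It does not. Under randomisation the unadjusted test's error rate already allows for chance imbalance.

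Third, adjustment is not the largest available gain. Analysing the factorial margins lowers the detectable difference at 80% power from 0.886 to 0.626 SD with no covariate. Adjusting for BMI at 20 vs 20 reaches only 0.767 SD even at r = 0.5. At 20 vs 20, power for a 0.6 SD effect stays below 60% throughout the range. This is correct, but the two steps are compatible and fit in one model.

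Finally, BMI could enter the planned regressions. Their stated purpose is to find influential factors, so this does not pre-specify an adjusted treatment effect.

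**Conclusion.** The point holds as an optional efficiency gain. Every named Substudy 4 group comparison is unadjusted, a plausible prognostic covariate is already held for all patients, and using it costs about one degree of freedom. For a 0.6 SD effect, the gain in power over r = 0.1 to 0.5 runs from nil to about 11 percentage points, both at 20 vs 20 (46% to 57%) and on the 40 vs 40 margins (75.5% to 86.4%). At r = 0.3 it is about 4 points. Both the effect size and r are assumptions, and the variance reduction applies to a linear model on log time only. The planned log-rank, ANOVA and Kruskal-Wallis tests are valid, and nothing here shows an error or a contradiction in the plan.

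**What to change.** Add a sentence to the Statistical Analysis Plan, before outcome data are examined by group. It should make the primary comparison of time to spontaneous eye opening a linear model on log time, with agent and M-Entropy guidance as the randomised factors and baseline BMI as a continuous covariate. Keep the Kaplan-Meier and log-rank analysis as the unadjusted supportive analysis.

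If censoring makes a Cox model necessary, use the same terms. Note that the gain there comes mainly from targeting a conditional hazard ratio and not from a 1 − r² reduction in variance, and that adjusted Cox rejected slightly too often in the 20 vs 20 null simulation.

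The cost is one sentence and about one degree of freedom. No new data are needed, and neither the sample size nor the randomisation changes.
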